### **Assessing Relationship to Study Treatment**

Items to be considered when assessing the relationship of an AE to the study treatment are:

- Temporal relationship of the onset of the event to the initiation of the study treatment
- The course of the event, especially the effect of discontinuation of study treatment or reintroduction of study treatment, as applicable
- Whether the event is known to be associated with the study treatment or with other similar treatments

- The presence of risk factors in the study subject known to increase the occurrence of the event
- The presence of nonstudy, treatment-related factors that are known to be associated with the occurrence of the event

*Classification of Causality*

The relationship of each AE to the study drug will be recorded on the CRF in response to the following question:

Is there a reasonable possibility that the study drug caused the AE?

Yes (related) A causal relationship between the study drug and the AE is a reasonable possibility.

No (not related) A causal relationship between the study drug and the AE is not a reasonable possibility.

#### 9.5.1.5.2 SERIOUS ADVERSE EVENTS AND EVENTS ASSOCIATED WITH SPECIAL SITUATIONS

An SAE is any untoward medical occurrence that at any dose:

- Results in death
- Is life-threatening (ie, the subject was at immediate risk of death from the adverse event as it occurred; this does not include an event that, had it occurred in a more severe form or was allowed to continue, might have caused death)
- Requires inpatient hospitalization or prolongation of existing hospitalization
- Results in persistent or significant disability/incapacity
- Is a congenital anomaly/birth defect (in the child of a subject who was exposed to the study drug)

Other important medical events that may not be immediately life-threatening or result in death or hospitalization but, when based on appropriate medical judgment, may jeopardize the subject or may require intervention to prevent one of the outcomes in the definition of SAE listed above should also be considered SAEs. Medical and scientific judgment should be exercised in deciding whether expedited reporting is appropriate in such situations.

In addition to the above, events associated with special situations include pregnancy or exposure to study drug through breastfeeding; AEs associated with study drug overdose, misuse, abuse, or medication error. These events associated with special situations are to be captured using the SAE procedures but are to be considered as SAEs only if they meet one of the above criteria. All AEs associated with special situations are to be reported on the CRF whether or not they meet the criteria for SAEs.

All SAEs must be followed to resolution or, if resolution is unlikely, to stabilization.

The following hospitalizations are not considered to be SAEs because there is no “adverse event” (ie, there is no untoward medical occurrence) associated with the hospitalization:

- Hospitalizations for respite care
- Planned hospitalizations required by the protocol
- Hospitalization planned before informed consent (where the condition requiring the hospitalization has not changed after study drug administration)
- Hospitalization for administration of study drug or insertion of access for administration of study drug
- Hospitalization for routine maintenance of a device (eg, battery replacement) that was in place before study entry

#### 9.5.1.5.3 LABORATORY MEASUREMENTS

Clinical laboratory tests to be performed are summarized in [Table 2](#). All clinical laboratory tests during the study will be performed by local laboratories. All hematology, blood chemistry (including pregnancy test, as applicable) are to be obtained prior to study drug administration and sent to the local laboratory on the day of collection, unless otherwise instructed. Subjects should be in a seated or supine position during blood collection.

**Table 2 Clinical Laboratory Tests**

Category	Parameters
Hematology	Hematocrit, hemoglobin, platelets, RBC count, and WBC count with differential (bands, basophils, eosinophils, lymphocytes, monocytes, neutrophils), INR a , PT a
Chemistry	Blood urea nitrogen (BUN), creatinine, aspartate aminotransferase, alanine aminotransferase, alkaline phosphatase, total bilirubin, lactate dehydrogenase, potassium, chloride, sodium, calcium total, cholesterol, total protein, albumin, total amylase, lipase, serum gamma glutamyl transpeptidase, C-reactive protein, ammonia.
Urinalysis/Urine Dipstick Testing	Glucose, hemoglobin (or blood), ketones, pH, protein, specific gravity
Other	$\alpha$ -Fetoprotein and thyroid-stimulation hormone Pregnancy test (serum or urine $\beta$ -hCG)

INR = International Normalized Ratio, PT = prothrombin time, RBC = red blood cell, WBC = white blood cell,

a: INR and prothrombin time (PT) should only be performed as part of the screening assessment and when clinically indicated.

The Schedule of Procedures/Assessments ([Table 3](#)) shows the visits and time points at which blood for clinical laboratory tests and urine for urinalysis will be collected in the study (refer to the Laboratory Manual for a list of tests). All hematology, blood chemistry (including pregnancy test, as applicable), and urinalysis samples are to be obtained prior to study drug administration and results reviewed prior to administration/dispensing of study drug at the beginning of each treatment cycle.

Laboratory tests at baseline may be performed up to 72 hours prior to start of study treatment. Hematology and clinical chemistry results will be reviewed within 48 hours after receiving quick estimation. Assessments scheduled may be performed within 72 hours prior to the visit. If subjects experience  $\geq$ Grade 3 hematologic or clinical chemistry toxicities, repeat laboratory tests and AE assessments at least every 7 days until improvement to  $<$ Grade 3. Refer to [Table 1](#) for the management of clinically significant laboratory abnormalities.

A laboratory abnormality may meet the criteria to qualify as an AE as described in this protocol (see [Section 9.5.1.5.1](#) and the CRF Completion Guidelines. In these instances, the AE corresponding to the laboratory abnormality will be recorded on the Adverse Event CRF.

For laboratory abnormalities meeting the criteria of SAEs ([Section 9.5.1.5.2](#)), the site must send the SAE report including the laboratory report (as regionally required) to the SAE fax number or email provided in the Investigator File.

#### 9.5.1.5.4 VITAL SIGNS AND WEIGHT MEASUREMENTS

Vital sign measurements (ie, BP [systolic and diastolic; mmHg], heart rate [beats per minute], respiratory rate [per minute], body temperature [in centigrade]) and BW (kg) will be obtained at the visits designated on the Schedule of Procedures/Assessments ([Table 3](#)) by a validated method. Blood pressure and heart rate will be measured after the subject has been resting for 5 minutes. All BP measurements should be performed on the same arm, preferably by the same person. One BP assessment is defined as the mean value of 2 measurements at least 5 minutes apart. If the BP assessment is elevated (systolic BP  $\geq$ 140 mm Hg or diastolic BP  $\geq$ 90 mm Hg), a confirmatory BP assessment at least 30 minutes later should be obtained by performing 2 measurements (at least 5 minutes apart) to yield a mean value.

Starting dose of lenvatinib is determined based on measurement of BW at the Baseline Visit. Subsequent measurements of BW are not relevant for dose determination.

#### 9.5.1.5.5 PHYSICAL EXAMINATIONS

Physical examinations will be performed as designated in the Schedule of Procedures/Assessments ([Table 3](#)). Documentation of the physical examination will be included in the source documentation at the site. Only changes from screening physical examination findings that meet the definition of an AE will be recorded on the Adverse Events CRF.

#### 9.5.1.5.6 ELECTROCARDIOGRAMS

A single resting 12-lead ECG will be performed as designated in the Schedule of Procedures/Assessments ([Table 3](#)). Complete, standardized, 12-lead ECG recordings that permit all 12 leads to be displayed on a single page with an accompanying lead II rhythm strip below the customary  $3 \times 4$  lead format are to be used. In addition to a rhythm strip, a

minimum of 3 full complexes should be recorded from each lead simultaneously. Subjects must be in the recumbent position for a period of 5 minutes prior to the ECG.

An ECG abnormality may meet the criteria of an AE as described in this protocol (see [Section 9.5.1.5.1](#)) and the CRF Completion Guidelines. In these instances, the AE corresponding to the ECG abnormality will be recorded on the Adverse Events CRF.

For ECG abnormalities meeting criteria of an SAE (see [Section 9.5.1.5.2](#)), the site must fax or email the SAE report including the ECG report to the sponsor using the SAE form (see [Section 9.5.4.1](#)).

#### 9.5.1.5.7 OTHER SAFETY ASSESSMENTS

Echocardiograms or MUGA scans will be obtained as designated on the Schedule of Procedures/Assessments ([Table 3](#)). A MUGA scan (using technetium-99m-pertechnetate) or an echocardiogram to assess LVEF will be performed during the Screening Visit and at the lenvatinib Off-Treatment Visit of the Lenvatinib Treatment Period (or sooner if clinically indicated). MUGA scans and echocardiograms should be performed locally in accordance with the institution's standard practice. MUGA scans are the preferred modality; however, whichever modality is used for an individual subject at baseline should be repeated for all subsequent LVEF assessments for that subject.

LVEFs as assessed by the institution will be entered onto the CRF. Investigator assessment will be based upon institutional reports.

#### Pregnancy Test

A serum or urine pregnancy test will be performed in women of childbearing potential (ie, premenopausal women and postmenopausal women who have been amenorrheic for less than 12 months) at designated time points as specified in the Schedule of Procedures/Assessments ([Table 3](#)).

#### 9.5.1.6 Other Assessments

Subjects perceived burden post lenvatinib treatment in the subsequent TPC period will be measured by completed PRO-CTCAE questionnaires. PRO-CTCAE data will be collected only at the lenvatinib Off-Treatment Visit in Treatment Period 1, and every 2 weeks for the first 4 weeks, and then at week 8 and week 16 ( $\pm 1$  week) in the TPC period. A TPC baseline assessment should be performed unless the lenvatinib Off-Treatment visit is completed within 7 days prior to the first TPC treatment.

#### 9.5.2 Schedule of Procedures/Assessments

##### 9.5.2.1 Schedule of Procedures/Assessments

[Table 3](#) presents the schedule of procedures/assessments for the study.

**Table 3 Schedule of Procedures/Assessments in Study E7080-M001-222**

Period	Screening a	Baseline a	Lenvatinib (Treatment Period 1) (All cycles are 28 days in duration)									TPC (Treatment Period 2)					Survival FU
			3	4	5	6	7	8, 9, etc		99							
Visit	1	2	Cycle 1 b		Cycle 2 c		Cycle 3 – Last c		Lenvatinib Off-Treatment Visit	TPC Baseline	Week 2	Week 4	Week 8	Week 16 aa	Every 12 weeks		
Day	-21 to -2	-1	1	8	15	1	15	1									
Procedures/ Assessments																	
Informed consent	X																
Inclusion/exclusion criteria	X	X															
Demographic data	X																
ECOG-PS d	X	X			X		X			X	X d	X	X	X			
NYHA d	X																
BCLC staging	X																
Medical/surgical history	X	X															
Gastroenterological endoscopy e	X																
Virus tests (HIV Ab, HCV Ab, HBsAg) f	X																
Phone contact or visit g				X													
Vital signs and weight h,i	X	X	X		X	X	X	X		X h	X	X	X				
Physical examination j	X	X k		X	X		X			X j	X	X	X				
12-Lead ECG l	X				X		X			X l	X	X	X				
MUGA scan or echocardiogram m	X									X							

Period	Screening a	Baseline a	Lenvatinib (Treatment Period 1) (All cycles are 28 days in duration)									TPC (Treatment Period 2)					Survival FU
			1	2	3	4	5	6	7	8, 9, etc		99					
Visit	1	2	3	4	5	6	7	8, 9, etc		99							
Day	-21 to -2	-1	Cycle 1 b			Cycle 2 c		Cycle 3 – Last c		Lenvatinib Off-Treatment Visit	TPC Baseline	Week 2	Week 4	Week 8	Week 16 aa	Every 12 weeks	
			1	8	15	1	15	1	15								
Procedures/ Assessments																	
Hematology and chemistry n	X	X			X	X	X	X		X	X n	X	X	X			
Urinalysis o,i	X	X			X	X	X	X	X	X	X i	X	X	X			
Pregnancy test p	X	X															
Child-Pugh score d	X	X			X		X			X	X d	X	X	X			
PRO-CTCAE questionnaires q										X	X q	X	X	X	X		
Blood coagulation test (PT/INR)	X	X			X		X			X							
Special chemistries r	X	X			X	X		X		X	X r			X	X		
Biomarker (whole blood) s		X															
Biomarker (serum/plasma) sample s			X		X	X		X		X	X s			X	X		
Tumor assessments CT/MRI t	X		CT of the chest and CT or MRI of the abdomen, pelvis, and other areas of known disease at screening plus newly suspected disease will be performed every 8 weeks from the first dose of study treatment, or sooner if clinically indicated, until disease progression. Triphasic CT/MRI of liver is									X	X t			X	X t

Period	Screening a	Baseline a	Lenvatinib (Treatment Period 1) (All cycles are 28 days in duration)									TPC (Treatment Period 2)					Survival FU																
Visit	1	2	3	4	5	6	7	8, 9, etc		99																							
Day	-21 to -2	-1	Cycle 1 b			Cycle 2 c		Cycle 3 – Last c		Lenvatinib Off-Treatment Visit	TPC Baseline	Week 2	Week 4	Week 8	Week 16 aa	Every 12 weeks																	
			1	8	15	1	15	1	15																								
Procedures/ Assessments			mandatory at screening and all subsequent time points.																														
Brain scan u	X		Brain scans will be performed if clinically indicated.																														
Archive tumor block or slides v	X																																
Survival w			Throughout														X																
Study treatment			QD for lenvatinib									TPC x																					
Prior/Concomitant medication y	Throughout																																
AEs/SAEs z	Throughout																																

AE = adverse event, BCLC = Barcelona Clinic Liver Cancer, CT = computed tomography, ECG = electrocardiogram, ECOG PS = Eastern Cooperative Oncology Group Performance Status, FU = Follow up, HBsAg = Hepatitis B surface antigen, HBV = hepatitis B virus, HCV Ab= hepatitis C virus antibody, HIV Ab = human immunodeficiency virus antibody, INR = international normalized ratio, MRI = magnetic resonance imaging, NYHA = New York Heart Association, MUGA = multigated acquisition, PRO-CTCAE = Patient-Reported Outcomes version of the Common Terminology Criteria for Adverse Events, PT = prothrombin time, SAE = serious adverse event, TPC = treatment of physician choice.

- a: Subjects must be screened within 21 days prior to the first dose of study treatment. The screening assessment can serve as the baseline assessment, if performed within 72 hours before the first dose of study treatment. The baseline assessments can be performed on C1D1, prior to the first dose of study treatment. Informed consent may be taken up to 4 weeks prior to C1D1.
- b: Efforts should be made to conduct study visits on the day scheduled ( $\pm$  1 day). Clinical laboratory assessments may be conducted anytime within 72 hours prior to the scheduled visit, unless otherwise specified in the Schedule of Procedures/Assessments.

- c: Efforts should be made to conduct study visits on the day scheduled ( $\pm$  3 days). Clinical laboratory assessments may be conducted anytime within 72 hours prior to the scheduled visit, unless otherwise specified in the Schedule of Visits and Procedures.
- d: See protocol appendices for ECOG assessments, NYHA Cardiac Disease Classification, and Child-Pugh assessments. NYHA cardiac disease classification should be only performed at Screening if needed. For ECOG and Child-Pugh assessments, a TPC baseline assessment should be performed unless the lenvatinib Off-Treatment visit is completed  $\leq$ 7 days prior to the first TPC treatment.
- e: Gastroenterological endoscopy at screening is necessary only if more than 3 months have passed since the previous assessment. Gastroenterological endoscopy must have been performed within 3 months prior to receiving first dose of the study treatment.
- f: Subjects who are receiving antiviral therapy for hepatitis B virus (HBV) may continue to receive this therapy at the discretion of the investigator.
- g: Telephone contact on or visit on C1D8 to assess subjects for development of early toxicity. An unscheduled visit will occur prior to C1D15 if deemed necessary by the investigator.
- h: Assessments will include vital signs (resting BP, heart rate, respiratory rate, and body temperature), and weight measured at Screening, Baseline, Day 1 and Day 15 of every cycle, lenvatinib Off-Treatment visit in Treatment Period 1, and at week 2, week 4, and week 8 ( $\pm$ 1 week) in TPC period. A TPC baseline assessment should be performed unless the lenvatinib Off-Treatment visit is completed  $\leq$ 7 days prior to the first TPC treatment. One BP assessment is defined as the mean value of 2 measurements at least 5 minutes apart. If the BP assessment is elevated (systolic BP  $\geq$ 140 mmHg or diastolic BP  $\geq$ 90 mmHg), a confirmatory BP assessment at least 30 minutes later should be obtained by performing 2 measurements (at least 5 minutes apart) to yield a mean value. Starting dose is determined based on measurement of body weight at the Baseline Visit. Subsequent measurements of body weight not relevant for dose determination. See dose adjustment table for management of hypertensive subjects.
- i: Subjects with systolic BP  $\geq$ 160 mmHg or diastolic BP  $\geq$ 100 mmHg must have their BP monitored every 2 weeks (on Day 15) or more frequently as clinically indicated until systolic BP has been  $\leq$ 150 mmHg and diastolic BP has been  $\leq$ 95 mmHg for 2 consecutive treatment cycles. If a new event of systolic BP  $\geq$ 160 mmHg or diastolic BP  $\geq$ 100 mmHg occurs, the subject must resume the Day 15 evaluation until systolic BP has been  $\leq$ 150 mmHg and diastolic BP has been  $\leq$ 95 mmHg for 2 consecutive treatment cycles.  
Urine dipstick testing for subjects with proteinuria  $\geq$ 2+ should be performed every 2 weeks (on Day 15) or more frequently as clinically indicated until the results have been 1+ or negative for 2 consecutive treatment cycles. If a new event of proteinuria  $\geq$ 2+ occurs, the subject must resume the Day 15 urine dipstick testing for evaluation of proteinuria until results are 1+ or negative for 2 consecutive treatment cycles.  
Note: During Cycle 3 and subsequent cycles in Treatment Period 1, subjects will return to the clinic for the Day 15 visit only if BP monitoring or urine dipstick testing is required as specified above. The Day 15 visit is mandatory in Cycles 1 and 2. In TPC period, a baseline urine dipstick testing should be performed unless the lenvatinib Off-Treatment visit is completed  $\leq$ 7 days prior to the first TPC treatment, and then the testing should be done at week 2, week 4, and week 8 ( $\pm$ 1 week).
- j: A comprehensive physical examination (including a neurological examination) will be performed at the Screening or Baseline Visit, on C1D15, on Day 1 of each subsequent cycle, and at the lenvatinib Off-Treatment Visit in Treatment Period 1 and at week 2, week 4, and week 8 ( $\pm$ 1 week) in TPC period. A TPC baseline assessment should be performed unless the lenvatinib Off-Treatment visit is completed  $\leq$ 7 days prior to the first TPC treatment. A symptom-directed physical examination will be performed on C1D1 and at any time during the study as clinically indicated. Height will be measured at the Screening Visit only.
- k: Required if screening physical examination is performed  $>$ 7 days prior to C1D1.

- l: Single 12-lead ECG. Subjects must be in the recumbent position for a period of 5 minutes prior to the ECG. ECG will be performed at week 2, week 4, and week 8 ( $\pm 1$  week) in TPC period. A TPC baseline assessment should be performed unless the lenvatinib Off-Treatment visit is completed  $\leq 7$  days prior to the first TPC treatment.
- m: MUGA or echocardiogram during screening and at lenvatinib Off-Treatment Visit or sooner if clinically indicated. Assessment should utilize the same methodology (MUGA or echocardiogram).
- n: Clinical laboratory tests (hematology and clinical chemistry) will be performed at local laboratory. Laboratory tests at Baseline may be performed up to 72 hours prior to first dose of lenvatinib treatment. Review hematology clinical chemistry results within 48 hours after receiving quick estimation. Assessments scheduled may be performed within 72 hours prior to the visit. If  $\geq$  Grade 3 hematologic or clinical chemistry toxicities, repeat laboratory test and AE assessment at least every 7 days (until improvement to  $<$ Grade 3). Clinical laboratory tests will be performed at week 2, week 4, and week 8 ( $\pm 1$  week) in TPC period. A TPC baseline assessment should be performed unless the lenvatinib Off-Treatment visit is completed  $\leq 7$  days prior to the first TPC treatment.
- o: For subjects with proteinuria  $\geq 2+$  (see the dose adjustment table for management of proteinuria).
- p: A serum or urine pregnancy test will be performed in women of childbearing potential (ie, premenopausal women and postmenopausal women who have been amenorrheic for less than 12 months). A separate baseline assessment is required if a negative screening pregnancy test was obtained more than 72 hours before the first dose of study drug.
- q: PRO-CTCAE data will be collected at the following time points: lenvatinib Off-Treatment Visit during Treatment Period 1, every 2 weeks for the first 4 weeks, and then at week 8 and week 16 ( $\pm 1$  week) in Treatment Period 2. A TPC baseline assessment should be performed unless the lenvatinib Off-Treatment visit is completed  $\leq 7$  days prior to the first TPC treatment.
- r:  $\alpha$ -Fetoprotein (AFP) and thyroid-stimulation hormone (TSH) will be measured at screening visit, Baseline, on C1D15, C2D1, C3D1, and every 2 cycles thereafter (C5D1, C7D1, C9D1, etc) in Treatment Period 1, and week 8 and week 16 ( $\pm 1$  week) in TPC period. A TPC baseline assessment should be performed unless the lenvatinib Off-Treatment visit is completed  $\leq 7$  days prior to the first TPC treatment.
- s: Collection of blood sample to obtain serum and plasma to be used for biomarker studies. Samples will be obtained on C1D1 (predose), predose on C1D15, Day 1 of and all subsequent cycles, and the lenvatinib Off-Treatment Visit in Treatment Period 1, and at week 8 and week 16 ( $\pm 1$  week) in Treatment Period 2 (TPC period). A TPC baseline assessment should be performed unless the lenvatinib Off-Treatment visit in Treatment Period 1 is  $\leq 28$  days before the first TPC treatment. A whole blood sample for genetic analysis will be obtained at baseline. If sampling is not performed predose, sampling may occur at any subsequent visit in which other blood sampling is scheduled to occur.
- t: Screening Period: Tumor assessments using triphasic liver CT/MRI (optimized for precontrast, arterial phase and portal venous phase), contrast-enhanced CT of the chest, and contrast-enhanced CT or MRI of the abdomen, pelvis, and other areas of known disease plus suspected disease should be performed within 28 days prior to first dose of study treatment.  
Treatment Period: Tumor assessments using triphasic liver CT/MRI (optimized for precontrast, arterial phase and portal venous phase), contrast-enhanced CT of the chest, and contrast-enhanced CT or MRI of the abdomen, pelvis, and other areas of known disease at screening or newly suspected disease should be performed every 8 weeks (during the 8th week) ( $\pm 1$  week) or sooner if there is evidence of progressive disease. The same methodology (CT or MRI) and scan acquisition techniques should be used as for the screening assessments.  
Tumor assessments will be performed during the Screening/Baseline Phase (standard of care scans performed up to 28 days before the first dose of study treatment are acceptable) and then every 8 weeks, or sooner if clinically indicated, during lenvatinib treatment phase until disease progression. Subjects

who discontinue lenvatinib treatment without disease progression should have tumor assessments performed (within one week of the lenvatinib Off-Treatment Visit) if more than 4 weeks have passed since the previous assessment and if the subject will not continue with follow-up scans.

Subjects entering subsequent treatment period (TPC period) should have TPC period baseline tumor assessments performed unless the last tumor assessment performed in lenvatinib treatment period is less than 28 days before the subsequent treatment starts, in which case those scans may be used as the TPC period baseline. A new tumor assessment baseline (selection of target and non-target lesions and calculation of a new baseline sum of diameters (SOD) must be established before beginning TPC. **Subjects will continue tumor assessments during subsequent TPC every 8 weeks ( $\pm 1$  week) or until disease progression, subject death, withdrawal or loss to follow-up.** Detailed image acquisition guidelines will be provided by the imaging core laboratory.

- u: Screening CT of the brain with contrast or MRI of the brain pre- and post-gadolinium should be performed within 28 days prior to the first dose of study treatment. During the study drug treatment period, CT/MRI of the brain should be performed if clinically indicated. The same methodology and scan acquisition techniques used at screening should be used throughout the study to ensure comparability.
- v: An archival tumor sample from the most recent surgery or biopsy for identification of predictive biomarkers and pathology review may be collected at screening or at any time during the study, unless no such material is available.
- w: Subjects who do not take subsequent TPC will be followed for survival every 12 weeks after the Off-Treatment visit. Otherwise, subjects will be followed for survival every 12 weeks after the final Visit in the subsequent TPC period. If a clinic visit is not feasible, follow up information may be obtained via telephone or email. Subjects' survival status and all additional anticancer treatments received will be recorded.
- x: Treatment dose and schedule on Prescribing Information of commercially available TPC should be followed.
- y: Concomitant meds will be recorded for 28 days after last dose of lenvatinib treatment if subjects do not enter TPC period, or for 8 weeks after the start of TPC period or up to 28 days after last dose of TPC if subject does not stay in the TPC period for the 8 weeks of safety monitoring. All anticancer therapy will be recorded until time of death or termination of survival follow-up. Prior medication information before screening should be collected at the screening period.
- z: SAEs irrespective of relationship to study treatment must be reported as soon as possible but not later than 1 business day. AEs will be recorded for 28 days after last dose of lenvatinib treatment if subjects do not enter TPC period, or for 8 weeks after the start of TPC period. During treatment interruption due to AEs, repeat AE assessment at least every 7 days (until restarting administration). SAE information should be collected for 8 weeks after the start of the TPC, or for at least 28 days after the last dose of lenvatinib/TPC if subjects do not continue into the TPC period or do not stay in the TPC period for the 8 weeks of safety monitoring.
- aa: After week 16, only tumor assessment and TPC dose information will be collected until the end of TPC (disease progression, development of unacceptable toxicity, subject request, withdrawal of consent, or study termination by the sponsor).

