##### 9.5.1.5.1 ADVERSE EVENTS

An AE is any untoward medical occurrence in a patient or clinical investigation subject administered an investigational product. An AE does not necessarily have a causal relationship with the medicinal product.

The criteria for identifying AEs in this study are:

- Any unfavorable and unintended sign (including an abnormal laboratory finding), symptom, or disease temporally associated with the use of an investigational product, whether or not considered related to the investigational product (Note: Every sign or symptom should not be listed as a separate AE if the applicable disease [diagnosis] is being reported as an AE).
- Any new disease or exacerbation of an existing disease. However, worsening of the primary disease (HCC) should be captured under efficacy assessments as disease progression rather than as an AE. If the disease progression leads to an untoward medical occurrence, then this medical occurrence should be recorded as an AE.

- Any deterioration in nonprotocol-required measurements of a laboratory value or other clinical test (eg, ECG or x-ray) that results in symptoms, a change in treatment, or discontinuation of study drug.
- Recurrence of an intermittent medical condition (eg, headache) not present pretreatment (Baseline).
- An abnormal laboratory test result should be considered an AE if the identified laboratory abnormality leads to any type of intervention, withdrawal of study drug, or withholding of study drug, whether prescribed in the protocol or not.

All AEs observed during the study will be reported on the CRF. All AEs, regardless of relationship to study drug or procedure, should be recorded beginning from the time the subject signs the study ICF through the last visit and for 28 days after the last dose of lenvatinib treatment if subjects do not enter TPC period, or for 8 weeks after the start of TPC period. SAE information should be collected for 8 weeks after the start of the TPC, or for at least 28 days after the last dose of lenvatinib/TPC if subjects do not continue into the TPC period or do not stay in the TPC period for the 8 weeks of safety monitoring.

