#### 9.7.1.1 Study Endpoints

##### 9.7.1.1.1 PRIMARY ENDPOINT

The primary endpoint is the safety and tolerability of subsequent systemic TPC following the first-line lenvatinib treatment in uHCC subjects, and will be analyzed by summarizing the incidence of treatment-emergent adverse events (TEAEs) and SAEs.

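### A compliant TPC Week 8 safety visit can fall up to 7 days after AE and SAE recording is stated to end, and the passages on that end point conflict

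*Combined protocol and SAP*

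**What the plan says.** **Visits.** Table 3, footnotes h, i, j, l and n, schedules vital signs, urine dipstick, physical examination, ECG and laboratory tests in the TPC period at Weeks 2, 4 and 8. For laboratory tests the text is "Clinical laboratory tests will be performed at week 2, week 4, and week 8", with the tolerance given as "week 4, and week 8 ( $\pm 1$ week) in TPC period". For ECG it is "ECG will be performed at week 2, week 4, and week 8", with the same tolerance. None of these five checks is scheduled at Week 16.

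**Recording.** Footnote z ends AE recording for subjects in TPC with the words "or for 8 weeks after the start of TPC period". For SAEs it says "SAE information should be collected for 8 weeks after the start of the TPC". Section 9.5.1.5.1 repeats both limits, and Section 9.5.4.1 repeats the SAE limit. None of the three places adds a visit tolerance.

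**Wording that points the other way.** Section 9.5.1.5.1 has AEs recorded "through the last visit and for 28 days after the last dose of lenvatinib treatment if subjects do not enter TPC period" before it gives the 8-week alternative. Table 3 marks the AE/SAE row as running throughout. After a Grade 3 or higher laboratory toxicity, footnote n requires sites to "repeat laboratory test and AE assessment at least every 7 days" until improvement, with no stop at 8 weeks.

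**Endpoint.** Under Section 9.7.1.1.1 the safety and tolerability of TPC "will be analyzed by summarizing the incidence of treatment-emergent adverse events (TEAEs) and SAEs". Neither that section nor the TEAE definition in Section 9.7.1.8.2 states a time limit.

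**The concern.** Week 4 to Week 8 is the longest interval between TPC safety visits: 4 weeks, against 2 weeks for each of the two before it. An abnormality without symptoms that arises in that interval may come to light only at the Week 8 visit. If AE recording has closed by then, whether the finding becomes an AE depends on the day the visit was booked rather than on what happened to the subject.

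The primary analysis is an incidence of recorded events, and the sample size is justified by the precision of a Grade 3 or higher TEAE rate. Under a rule with two readings, sites could handle identical findings differently, and the dataset would not show which reading each had used. The concomitant-medication window has the same 8-week limit (Section 9.4.7, footnote y, Section 9.7.1.5), so treatment started at a late Week 8 visit could go unrecorded as well.

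**Working it through.** **1. The plan's own figure.** Table 4 uses the Wald half width, 1.96 × √(0.75 × 0.25 / n), with n the number receiving TPC.

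| n | Computed | Table 4 |
|---|---|---|
| 100 | 8.49% | 8.5% |
| 90 | 8.95% (8.946 before rounding) | 8.9% |
| 80 | 9.49% | 9.5% |
| 70 | 10.14% | 10.1% |
| 60 | 10.96% | 11% |
| 50 | 12.00% | 12% |

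The table reproduces. It contains no time window, so this point does not affect it.

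**2. Day count, with one common origin as day 0.**
- Week 8 visit: 56 ± 7, so days 49 to 63, which is 15 calendar days.
- Stated end of AE and SAE recording: 8 × 7 = day 56.
- Compliant visit days after that end: 57 to 63, which is 7 of 15 (47%). Visits on days 49 to 56 have no gap.
- Footnote n lets scheduled assessments be done up to 72 hours before the visit. Laboratory samples for a visit on days 57 to 59 could thus be taken on days 54 to 56. This narrows the laboratory gap where sites use the allowance, but does not close it for days 60 to 63.

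**3. Route to the endpoint.** Under Section 9.5.1.5.1 a laboratory abnormality is an AE if it leads to an intervention or to withholding or withdrawing drug. For a silent abnormality found on day 60, both identification and intervention come after day 56. The value still enters the by-visit summaries and, for laboratory tests, the CTCAE shift tables (Section 9.7.1.8.3). It enters the TEAE incidence only if someone records an AE. No section says whether the cut-off applies to onset or to detection. An event with documented onset by day 56 may be recordable; an abnormality known only from a day-60 sample has no documented onset before day 60.

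**4. Size, as an illustration only.** Let q be the share of TPC subjects whose only Grade 3 or higher TEAE is first found at the Week 8 visit. The documents give no value for q. If visits spread evenly over the window and every finding after day 56 is dropped, the loss is q × 7/15:
- q = 5%: 2.3 points
- q = 10%: 4.7 points
- q near 0: near 0

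The assumption that every late finding is dropped makes this the unfavourable end for a given q.

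**5. Clock origin.** AEs run from the start of the TPC period, which Sections 9.1.2.2 and 9.4.1.2 place at completion of the lenvatinib Off-Treatment Visit. SAEs run from the start of TPC. If the first TPC dose comes D days after that visit, the literal AE limit falls on TPC day 56 − D, and the gap to the latest compliant visit is 63 − (56 − D) = 7 + D days, if visits are counted from the first dose. TPC may start 8 weeks or more after the Off-Treatment Visit, following discussion with the sponsor. At D = 56 the literal AE window would be used up at the first dose.

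**6. Effect of a longer window.** Suppose the assumed 75% is the cumulative rate at 8 weeks (an assumption; no window is stated). If every subject were followed to week 9, the rate would be 1 − 0.25^((9/8)^k), with k a Weibull shape:
- k = 0.5: 77.0%
- k = 1: 79.0%
- k = 1.25: 79.9%

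That is 2.0 to 4.9 points more. The half width at n = 50 would be 11.7% to 11.1%, still within the planned 12%.

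**The case against.** The strongest reply is that the protocol as a whole does not close recording on day 56. Section 9.5.1.5.1 has all AEs observed during the study reported and refers to the last visit. Table 3 runs the AE row throughout. Sections 9.5.1.5.3, 9.5.1.5.5 and 9.5.1.5.6 send laboratory, examination and ECG findings that meet AE criteria to the AE form, with no 8-week exception. Footnote n expects continued AE assessment after a severe laboratory toxicity. Section 9.5.4.1 keeps lenvatinib-related SAEs reportable without limit.

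Much of this stands: it makes the cut-off ambiguous and suggests that recording at the visit was intended. It does not settle the matter. The sentence in Section 9.5.1.5.1 ends with the 8-week limit, and footnote z leaves out the last visit altogether. The last visit cannot simply mean the last TPC visit, because TPC visits continue to Week 16 and scans go on after that. The open-ended SAE rule covers lenvatinib and protocol procedures, not TPC.

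A reader might infer that recording certainly stops on day 56, that findings from any in-window Week 8 visit fall outside the primary endpoint, or that the primary rate is understated by a known amount. The documents do not support these readings. The first is only the literal sense of footnote z. As to the second, only days 57 to 63 are exposed, and the endpoint and TEAE definition carry no 8-week limit, so any loss would come through non-recording. The third needs q, which is not given.

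**Conclusion.** The mismatch is real and minor. The last scheduled TPC safety visit may be up to 7 days later than the stated end of AE and SAE recording, and the relevant passages disagree on whether that end is firm. Events may be lost from the Period 2 TEAE incidence only where the visit falls on days 57 to 63, the finding was not known before, and the site follows the 8-week limit literally. The size of any loss cannot be derived from the documents and is probably small.

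The day count assumes one origin for visits, AEs and SAEs. The protocol does not state one, and under its literal definition of the TPC period the AE gap could be larger. Section 9.7.1 leaves detail to a separate SAP; no SAP text in the document reviewed sets the Period 2 TEAE window, so it cannot be checked whether that plan resolves the point.

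**What to change.** In Section 9.5.1.5.1, Section 9.5.4.1 and Table 3 footnote z, state that AE and SAE recording in TPC runs to the later of 8 weeks after the first TPC dose or the actual Week 8 safety visit, at latest day 63. Keep the existing 28-day provisions for subjects who do not enter TPC or leave it early. The later-of rule matters: ending recording at the Week 8 visit alone would cut it short for anyone seen on days 49 to 55.

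In the same edit:
- Use the first TPC dose as the single origin for visits, AEs and SAEs, and reconcile Sections 9.1.2.2 and 9.4.1.2 with it.
- State that an event is in the window if its onset or first detection falls on or before that end point.
- Carry the window into the Period 2 TEAE definition (Section 9.7.1.8.2) and the concomitant-medication rules (Section 9.4.7, footnote y, Section 9.7.1.5).

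The cost is wording in these places and at most 7 more days of recording, up to a visit already scheduled. The disadvantage is an AE window that varies from 56 to 63 days between subjects. Some events recorded in the added days will be new rather than late-found, so the report should give the distribution of window lengths.
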